Aim4: To assess feasibility, acceptability, user-friendliness, perception of benefit, and improved scar cosmetic appearance

H4: CDO adjunct therapy will be considered to be practical to use, easy to use, and is perceived to be beneficial from both practitioner and subject as assessed by user friendliness questionnaire adapted for the purpose of this study (assessment at the conclusion of the study). This questionnaire is attached to the protocol.

H5. CDO adjunct therapy will improve scar cosmetic appearance as assessed by practitioner using the Scar Cosmesis Assessment and Rating (SCAR) Scale.

Section E: Protocol Risks/Subjects

E1. Risk Category

Category 2: Research involving greater than minimal risk, but presenting the prospect of direct benefit to the individual subjects.

E2. Subjects

Gender:

Both

Age:

```
Adult (18-64 yrs), Geriatric (65+ yrs)
```

Ethnicity: All Ethnicities

Primary Language: English, Spanish

Groups to be recruited will include: Patients

Which if any of the following vulnerable populations will be recruited as subjects?

Vulnerable populations require special protections. How will you obtain informed consent, protect subject confidentiality, and prevent undue coercion?

E3. Pregnant woman/fetus

Will pregnant women and/or fetuses (as described in 45 CFR 46 Subpart B) be enrolled in the research? No

E4. Neonates

Will neonates of uncertain viability or nonviable neonates (as described in 45 CFR 46 Subpart B) be enrolled in the research? No

E5. Children

Will children be enrolled in the research?

Section F: Design/Procedure

F1. Design

Select one category that most adequately describes your research:

c) Pilot

Discuss the research design including but not limited to such issues as: probability of group assignment, potential for subject to be randomized to placebo group, use of control subjects, etc.

This study will be a 4 weeks prospective, exploratory internal randomized controlled trial study to test feasibility, acceptability, and proof of concept efficacy of Continuous Diffusion of Oxygen (CDO) adjunct therapy for decreasing healing time and reducing wound dehiscence post reduction mammoplasty. The anticipated sample size is N=30, who are undergoing bilateral reductive mammoplasty surgical procedure.

The study visits are listed below (please note that no screening activities will take place prior to the patient signing a consent form):

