1) Baseline (Surgery Day, Week 0) 2) Visit 1 (Week 1 Post-Op) 3) Visit 2 (Week 2 Post-Op) 4) Visit 3 (Week 3 Post-Op) 5) Visit 4 (Week 4 Post-Op) 6) Visit 5 (minimum of 6 months Post-Op) *optional

Baseline: Subjects will be randomized to internal control. Since all procedures are bilateral, an internal randomization will be performed based on breast side (left or right). The patients will be given CDO in one breast defined as intervention breast. A 5x5 cm CDO dressing will be placed by the plastic surgeon over the T-inframammary fold after the Dermabond glue and Prineo tape are placed. Then, Silagen (a silicon sheet) will be placed on top of the CDO dressing to secure it in place. The remaining parts of the incision will be covered with Dermabond Glue and Prineo tape. On the contrary, the control breast will be given the standard dressing (Dermabond + Prineo tape).

Visits 1-4: All patients will have baseline assessment including visual, dermal, and tissue oxygen saturation level. The status of wound closure and presence of wound complication will be monitored every week. Each subjects will need up to 5 visits including baseline assessment, and weekly assessment up to 4 weeks or full wound healing or surgical revision, whichever comes first. At each visit, patients will be provided standard of care treatment including regular wound dressing change. Table 1 in attachments' section summarizes the key measurement at each study visit. At Visit 4, the CDO therapy will be removed. Subjects will then have the option to return at minimum 6 months later for a final follow-up visit listed below.

Visits 5: Optional follow-up visits. This visit can also be done remotely should the person not be available to attend the clinic.

Inclusion Criteria:

18-85 years of age. Ability to provide informed consent. Presence of a wound due to surgical intervention and closure. Subject or responsible caregiver is willing and able to maintain the required Continuous Diffusion of Oxygen (CDO) system (if assigned to the intervention group) and applicable dressing changes

Exclusion Criteria:

Active Drug/alcohol abuse (or history of drug/alcohol abuse in last 1 month); excessive lymphedema; presence of active infection; subject has a history of or any intercurrent illnesses or conditions that would compromise the safety of the subject according to judgement of a qualified wound specialist.

F2. Procedure

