Wound Assessment (primary outcome): A digital photo/video of wound will be taken for wound size verification, estimation of wound size, success of wound healing, and determination of wound dehiscence. Measurement will be performed at every visit.

Pain Intensity Assessment (VAS) (secondary outcome): The subject will be provided with a numeric pain scale where he/she will report pain intensity. Research staff will document subject's pain level. (Collected at every visit)

Adverse Event Reporting: Research Staff will document and report any study/non study related incident as per institution regulations. (Collected at baseline and visits 1-4)

Device Acceptability Questionnaire: To determine patient perception of benefit, perceived ease of use, and attitude toward the use of device, we will use a technology acceptance model (TAM) questionnaire tailored for the purpose of this study. This assessment will be done at the conclusion of the study (week-4)

Questionnaires (optional): Quality of Life (PROMIS), functional status, Frailty Status (TSFI), Cognitive Assessment, and Sleep Quality (PSQI). To evaluate functional status, we will use well accepted and validated general functional assessment instruments. PFIBS for Pain Frequency, Intensity and Burden Scale, MOCA for Mental Exam, and Visual analog scale for pain. (All questionnaires are optional and may be done at any study visit upon time availability and patient acceptability). We will add the already approved questionnaires for the parent study, which include pain. Additionally, we will include Likert Scales (Moon SH et al, 2011; Singer AJ et al 1997; Hollander JE et al 1995; and Ridway DM et al 2007) and Patient Attitude to Scarring Scale (PASS, Kantor J et al 2016) and Patient and Observer Scar Assessment Scale (POSAS) to assess the following patient-reported outcomes: patient satisfaction and cosmetic appearance to evaluate scar itchy, perception of scar thickness, scar discomfort, and pain for each wound side (i.e., left and right breast). SCAR may be used to assess plastic surgeon satisfaction with the scarring. These questionnaires will be answered to the best of the participant's abilities. Should the participant lack certain capacities that make it difficult for them to respond to these questionnaires, they will not be conducted with that participant.

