The primary outcomes of this study are 1) tissue oxygen saturation level measured using Kent Imaging system and 2) incident of wound related adverse events (e.g., incident wound dehiscence, infection, scar size, and surgical revision). Secondarily outcomes include pain, wound outcomes (e.g. wound size, scar size, wound healing rate, etc assessed using digital photography), area of inflammation (assessed using KENT), and pain (assessed using VAS). Exploratory outcomes include patient quality of life, sleep quality, anxiety, and depression. Baseline between group comparison will be dine using two-sample t-tests, Mann-Whitney U-test, or Chi-square depend on scale/distribution of the variables (i.e., parametric, non-parametric, or binary). We will use general mixed linear model and post-hoc analysis to examine difference between

groups (time, group, and time X group effect) for skin perfusion. We will adjust the results based on baseline incision wound size and duration between baseline and last visit assessment. Subjects with at least one week continue treatment will be included in the analysis. Controlled variables include age, BMI, baseline vascular health. We will use chi-square to estimate whether the number of wound complication incidents is less in the intervention group compared to the control group. Chi-square or repeated ANOVA or Mann-U test depend on scale/distribution of the variable will be used for secondary and exploratory outcomes.

Section H: Potential Risks/Discomforts

H1. Potential Risks/Discomforts

Describe and assess any potential risks/discomforts; (physical, psychological, social, legal, or other) and assess the likelihood and seriousness of such risks:

As any new investigational device, there are some risks, which are anticipated to be minimal in this study. Some of potential risks could be: * Skin related discomfort, erythema (redness), skin rash, dryness and itching. * Skin allergic reaction to dressing adhesive. * Tenderness/minor ache around the dressing application area * Heat sensation and/or perspiration with wearing dressing * Some impairment of mobility due to dressing unit

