Some of the study devices (OxyGeni, KENT) and technology are completely non-invasive, safe, non-toxic and nonionizing. The potential risks are minimal. However, like any battery powered systems, there is a minimum risk of sensor malfunctioning. In addition, the study devices are not waterproof, and although they use a low powered battery (similar to a cell-phone battery), in order to avoid any risk of shock the monitor should not be submerged or saturated with fluids during operations or cleaning.

When wearing the study devices, there is a small risk of tripping. The dressing will be connected to the OxyGeni device through a thin tube that will be placed comfortably along the subject's legs underneath their clothing. We will instruct the subject to place the tube correctly to minimize any risk of tripping.

Subjects must be willing to charge device battery daily. Otherwise they will not receive benefit from treatment. OxyGeni is a wireless chargeable device to increase patient comfort.

The assessments described above are expected to be minimal risk and probability and magnitude of harm or discomfort anticipated in the research are not greater in and of themselves than those ordinarily encountered in daily life or during the performance of routine physical or psychological examinations or tests.

Please note that there is also the possibility for loss of confidentiality. The PI and the research team will minimize the possibility of for loss of confidentiality by keeping all the physical data locked in cabinets only accessible to the research team. The electronic data will be kept on network password protected institutional computers. Data collected during the study may be published and made publicly available. Data may also be shared with other research groups. However, data that could in any way identify the subject will not be made public or shared. And, subject PHI will be coded as much as possible to minimize the potential for loss of confidentiality.

H2. Data and safety monitoring plan

Do the study activities impart greater than minimal risk to subjects? Yes

NOTE: The answer to the questions in H2 requires the completion of the form: 'Section H â€" Data and Safety Monitoring Plan' as an attachment in Section S.

H3. Coordination of information among sites for multi-site research

Is the BCM Principal Investigator acting as the SPONSOR-INVESTIGATOR for this multi-site research? No or Not Applicable

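### Device acceptability is scheduled only at week 4, with no provision for patients who stop or leave earlier, so the result may be weighted to those who tolerated the device

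*Combined protocol and SAP*

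**What the plan says.** Section D names feasibility and acceptability first among the purposes of the trial and makes them Aim 4: "Aim4: To assess feasibility, acceptability, user-friendliness, perception of benefit, and improved scar cosmetic appearance". H4 expects that the therapy "is perceived to be beneficial from both practitioner and subject as assessed by user friendliness questionnaire", and gives the timing only as the end of the study: "user friendliness questionnaire adapted for the purpose of this study (assessment at the conclusion of the study". In F2 the Device Acceptability Questionnaire, a tailored technology acceptance instrument, is timed once: "This assessment will be done at the conclusion of the study (week-4". The freedom to use any study visit, also in F2, belongs to the separate item on optional questionnaires, which does not list this instrument.

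Several other provisions bear on who will be asked:

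- F1 schedules "weekly assessment up to 4 weeks or full wound healing or surgical revision, whichever comes first", so a subject's assessments can end before week 4.
- J2 allows withdrawal at any time. No exit assessment is described.
- G2 states: "Subjects with at least one week continue treatment will be included in the analysis".
- H1 describes the burden on the patient: "Subjects must be willing to charge device battery daily. Otherwise they will not receive benefit from treatment".
- The task lists for visits 1 to 4 in F2 include device education and adverse event reporting. They contain no item for days of device use, dressing dislodgement, or the date of and reason for stopping CDO. Table 1, which F1 cites for the measurements at each visit, is an attachment that was not supplied.

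**The concern.** A single end-of-study questionnaire measures acceptability among those who are still there to answer it. The device is worn for four weeks, tubed and charged daily. Patients who find that too much are the ones most likely to stop, and some of them may also leave the study or miss visit 4. If their answers are missing, the result leans toward easy to use and beneficial.

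The supplied text offers no second source that would show this had happened. Without a record of device use and stop reasons, the report cannot say how many of the 30 kept using CDO, or why the others did not. The one-week rule adds to the selection: read literally, it removes the earliest stoppers even if someone did ask them. G2 lists neither acceptability nor feasibility among its outcomes and sets no denominator for either.

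This matters because feasibility is a lead purpose of the pilot, and G1 says the sample may be enlarged on the strength of the initial results.

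**Working it through.** The documents give no acceptability target, dropout rate or stop rate, so there is no figure of the plan's own to reproduce. The check has two parts.

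**1. Who can be missed, from the text**

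| Patient | Reaches the week-4 questionnaire? | Likely direction if missed |
|---|---|---|
| Uses CDO to week 4 | Yes | None |
| Stops CDO but attends visit 4 | Can be asked; nothing says otherwise | None if asked |
| Stops CDO for burden and withdraws or misses visit 4 | Not provided for | Upward bias |
| Ends assessment early through healing | Not stated | Unclear; may well be favourable |
| Ends assessment early through revision | Not stated | Unclear |
| Under one week of treatment | May be asked, but outside the analysis as G2 is worded | Upward if stopped for burden |

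Early ends through healing are foreseeable. Section C says incisions are normally healed once the tape comes off at 3 weeks.

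**2. How large the effect could be**

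Input from the documents: N = 30 (G1). Assumptions: m patients are not asked, with m = 3, 6 or 9, and a proportion p = 0.80 of those asked is favourable.

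- Reported rate: p.
- Worst case over all 30 (every missed patient unfavourable): p(30 − m)/30.
- Best case over all 30 (every missed patient favourable): [p(30 − m) + m]/30.
- Maximum overstatement: p − p(30 − m)/30 = p × m/30.

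| m | Reported | Worst case | Best case | Maximum overstatement |
|---|---|---|---|---|
| 0 | 80% | 80% | 80% | 0 |
| 3 | 80% | 27 × 0.8/30 = 72% | (21.6 + 3)/30 = 82% | 8 points |
| 6 | 80% | 24 × 0.8/30 = 64% | (19.2 + 6)/30 = 84% | 16 points |
| 9 | 80% | 21 × 0.8/30 = 56% | (16.8 + 9)/30 = 86% | 24 points |

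Whole-number counts near 80% give the same picture: 22/27 = 81.5% against 22/30 = 73.3%; 19/24 = 79.2% against 19/30 = 63.3%; 17/21 = 81.0% against 17/30 = 56.7%. The maximum overstatements are 8.1, 15.8 and 24.3 points. If about 90% of those asked are favourable, the maxima are about 9, 18 and 27 points.

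Only patients who are not asked count toward m. If 6 stop CDO and 3 of them still attend visit 4, then m = 3 and the bound falls from 16 to 8 points.

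At least one early stopper is likely even at a low assumed individual probability q. The chance among 30 is 1 − (1 − q)^30, which is 79% for q = 5%, 96% for q = 10% and over 99% for q = 20%. These q values are assumptions, and stopping is not the same as being missed.

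**The case against.** The strongest reply is that nothing in the documents makes stopping the device the end of follow-up. Visit 4 is described for all patients. Section L bills a post-operative visit at visits 0, 2 and 4 as standard of care and pays for each in-person visit, and F2 allows home visits to fix device problems. A patient who gives up CDO therefore has ordinary reasons to attend at week 4 and can be asked there. This stands. A reader might infer that early stoppers are never asked, or that the plan followed exactly yields a rate among completers only. The text does not support either.

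Three further replies also stand in part:

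- **Direction.** A patient whose assessment ends because the wound healed has no evident reason to dislike the device. Losing such patients could even lower the result. The upward bias comes from stops for burden or intolerance, not from every early end.
- **Timing.** H4 itself says only the conclusion of the study, which could be read as each subject's own last visit. F2, however, attaches week 4 to it, so staff following F2 have no instruction to ask earlier.
- **Other evidence.** H4 also takes the practitioner's view, and adverse events are recorded at baseline and visits 1 to 4. Table 1 and the questionnaire are attachments, so a further time point or a device-use field there cannot be excluded. It would therefore be too strong to say that every route to a feasibility answer is closed. Even so, neither adverse events nor practitioner opinion shows how many of the 30 patients kept using the device.

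Finally, the questionnaire is not listed among the primary, secondary or exploratory outcomes, and no acceptability threshold is set. A percentage favourable is thus a convenient summary for illustration, not a quantity that the plan defines.

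**Conclusion.** The gap is real and worth closing. Acceptability has one stated time, the supplied text does not provide for patients who stop, withdraw or finish early, device use and stop reasons are not among the visit procedures, and the one-week rule narrows the analysis further. The result may therefore be weighted to patients who tolerated the device.

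How far it would be is unknown, because the documents give no stop rate. The effect is zero if everyone is asked. It is at most about 8, 16 or 24 points if 3, 6 or 9 of 30 are missed, every one of them is unfavourable, and 80% of those asked are favourable. These are upper bounds on assumed figures, not expected values. With best-case answers from the missed patients, the reported 80% would instead be 2, 4 or 6 points too low. Early ends through healing have no clear direction. The finding is subject to Table 1, which was not available.

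**What to change.** Three changes:

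1. **Timing (F2).** Schedule the acceptability questionnaire *at week 4, or at the visit or call at which CDO is stopped or the subject leaves the study, if earlier*. Align the wording of H4 and the visit 4 task list, which at present does not name the questionnaire.
2. **Data at visits 1 to 4.** Record days the device was off or uncharged, dressing dislodgement, and the CDO stop date and reason.
3. **Reporting (G2).** Report acceptability and CDO continuation descriptively for all randomised patients, exempt from the one-week rule. Show the number not asked, with best-case and worst-case bounds. List stops for healing or revision separately from stops for burden or intolerance.

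A stop should not be scored automatically as not acceptable, since that would replace the patient's own answer. Nor should a patient who finishes early through healing be counted as a feasibility failure.

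The cost is a few case report form lines at existing visits and an earlier questionnaire for the few patients concerned. The downside is that the reported acceptability figure may be lower. Answers and reasons not collected at the time cannot be reliably recovered afterwards.

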A9. ClinicalTrials.gov Registration

Does this protocol/trial require registration on ClinicalTrials.gov due to it: meeting the definition of an Applicable Clinical Trial, being required under the terms and conditions of an award, or being proposed to be published in ICMJE journals? Yes

Who will be responsible for registering and maintaining the registration of this Applicable Clinical Trial? The BCM PI will register the trial because either:

- the trial is BCM PI-initiated,
- BCM is the lead site of this multicenter trial, or,
- the industry sponsor has instructed the BCM PI to register the trial, or,
- registration of this trail is required as a term and condition of the reward by the funding agency.

ClinicalTrials.gov Identifier: NCT04307355

Section B: Exempt Request

B. Exempt From IRB Review

Not Applicable

Section C: Background Information

Reduction mammoplasty is a procedure in which a volumetric reduction of the breast is done for cosmetic purposes. This technique includes an infra-mammary perpendicular incision joined by a T-inframammary fold in it; central area, that further continue vertically until surrounding the nipple perimeter.

The likelihood of poor healing outcomes and adverse events (e.g., wound dehiscence, thick scar, itchy or unsortable scars) at the T-inframammary fold (anchor incision) of the breast wound incision is relatively high (estimated to be 10%-15%). This pure outcome is attributed to the corner (as a result of the T-inframammary fold) low blood supply. Given the fact that there are two corners in this particular procedure, the chances of adverse events are higher due to the point of most tension for the entire breast. Continuous oxygen therapy may reduce the likelihood of poor outcomes and adverse events.

In our institution, the Plastic Surgery Department utilizes Dermabond glue (sano acrylic) and Prineotape (air and water sealed) to close the wound around the areola and over the T-inframammary fold. Depending on the incision size, a JP drain could be placed (10% of the cases). Furthermore, the Prineo tape is kept on for a period of 3 weeks. Once it is removed, the incisions are normally healed. However, if wound dehiscence presents, it normally happens between the second and third post-operative week. Then, the Prineo tape has to be removed before the expected time period. Therefore, an external dressing might be able to avoid wound dehiscence during this period.

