Continuous Diffusion of Oxygen (CDO) is a treatment modality that delivers pure oxygen to wounds using the same basic mechanism as breathing, namely direct diffusion into the wound from a moist surface. Because impaired blood flow results in impaired oxygen supply to incisional wounds, investigators have researched the potential of oxygen saturation, or supersaturation, to reinitiate or even accelerate wound healing. Oxygen has been shown to result in not only faster wound closure, yet also better strength of repair and higher organization of collagen, which in turn can result in lower wound recidivism and better scar appearance.

In this feasibility and proof of concept study, we plan to investigate the effects of oxygen on incisional wound repair and scarring after mammoplasty. We will use a device (OxyGeni Oxygen Delivery System) which continuously supplies oxygen to the wound inside the wound dressing. The device we used, the OxyGeni System, (EO2 Concepts®, San Antonio, TX) is small, wearable and silent. The system is FDA-approved and CDO therapy has been the subject of a growing body of clinical experience and scientific investigations demonstrating good results. The therapy is similar in theory to the intermittent application of oxygen through Hyperbaric Oxygen (HBO) and Topical Oxygen (TO), with a few key differences summarizing in the following:

1) CDO provides continuous therapy, providing ~twenty-fold longer time of oxygen delivery versus intermittent therapies that are only applied 90 minutes a day. 2) CDO allows for full patient mobility during treatment, thereby reducing the risk of non-compliance and reducing overall costs

We have successfully used CDO therapy to reduce likelihood of tissue necrosis after surgical closure post lower extremity amputation as well as post anterior neck surgery, in which over 20 subjects were recruited and no adverse outcomes were reported. We plan to extend our study to determine whether CDO therapy would show decreased healing time and improved scar appearance early on for standardized incisional wounds such as breast reconstruction. We hypothesize that using CDO will reduce the likelihood of wound dehiscence as well as severe incisional scar post-surgical closure by improving transcutaneous oxygen levels during wound healing process. We will examine the validity of this hypothesis using a pilot randomized controlled trial using a convenient sample of 30 women undergoing bilateral mammoplasty.

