Section D: Purpose and Objectives

This is an exploratory randomized controlled trial study to test feasibility, acceptability, and proof of concept efficacy of Continuous Diffusion of Oxygen (CDO) adjunct therapy for decreasing healing time and reducing tissue dehiscence post breast reconstruction. We will assess the benefit of this novel adjunct therapy on successful closure, tissue oxygenation, scar appearance, and patients centered outcomes including perception of benefit, pain, sleep quality, and quality of life. Since all procedures are bilateral, an internal randomization will be performed based on breast side (left or right). The patients will be given CDO in one breast defined as intervention breast. A 5x5 cm CDO dressing will be placed by the plastic surgeon over the T-inframammary fold after the Dermabond glue and Prineo tape are placed. Then, Silagen (a silicon sheet) will be placed on top of the CDO dressing to secure it in place. The remaining parts of the incision will be covered with Dermabond Glue and Prineo tape. On the contrary, the control breast will be given the standard dressing (Dermabond + Prineo tape). The study device OxyGeni is a Class II medical device which has US Food and Drug Administration (FDA) 510(k) clearance, CE-Mark approval and a Health Canada license for the treatment of wounds.

Outcomes will be assessed on weekly-basis up to 4 weeks. Here are the aims and hypotheses for this study:

Aim1: To assess effectiveness of CDO adjunct therapy in reducing the likelihood of wound complication post-surgical

closure.

H1: CDO adjunct therapy will reduce the likelihood of surgical wound complication including dehiscence and its volume, infection or surgical revision, compare to standard of care dressing.

Aim2: To assess changes in skin perfusion in patients treated with CDO adjunct therapy.

H2: CDO adjunct therapy will improve tissue oxygen saturation in >50% of the patients as compared to baseline (measurements at baseline, 2 weeks, and 4 weeks).

Aim3: To evaluate changes in quality of life, anxiety during dressing change, and psychosocial parameters in patients with a surgical wound treated by CDO adjunct therapy

H3: CDO adjunct therapy will improve subject quality of life, reduce anxiety, and reduce perceived pain and physiological stress response during dressing change compared to the control group.

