Visit 5, at minimum 6 months post-op *duration: 50 minutes. This is an optional visit where research staff will take a NIRS image, a Digital Photograph, report adverse events since last visit, and assess patient scar satisfaction using validated questionnaires (PASS and POSAS). Moreover, the plastic surgeon will provide their observation of the scarring using validated questionnaires (SCAR and POSAS). The patient will be seen in the Vascular Clinic (Procedure Room). Female research coordinator will perform all measurements and questionnaires under ethics protocol. Should the patient not be available to attend the clinic in-person, they will have the option to do the questionnaires remotely and upload digital photos of the area via RedCAP. This study visit is added to provide long-term information regarding scarring and effect of study device on long-term healing outcomes.

The research coordinator will make sure at all times that patient does not experience discomfort and all ethical protocols will be followed.

Section G: Sample Size/Data Analysis

G1. Sample Size

How many subjects (or specimens, or charts) will be used in this study? Local: 30 Worldwide: 30

Please indicate why you chose the sample size proposed:

This is an exploratory proof of concept study. The anticipated sample size (n=30) is selected based on resource/budget availability and feasibility to be completed within one year. This sample size is estimated to be sufficient to determine feasibility and proof of concept efficacy of Continuous Diffusion of Oxygen (CDO) adjunct therapy to improve tissue oxygen supply and reduce likelihood of adverse events. Upon initial results and availability of budget, the sample size may be increased to clinically validate the initial observation. In this case, an addendum will be submitted to increase sample size if needed.

G2. Data Analysis

Provide a description of your plan for data analysis. State the types of comparisons you plan (e.g. comparison of means, comparison of proportions, regressions, analysis of variance). Which is the PRIMARY comparison/analysis? How will the analyses proposed relate to the primary purposes of your study?

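### The chi-square planned in G2 for wound complications ignores the left/right pairing, and G1's statement that n=30 is sufficient for adverse events has no estimate behind it

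*Combined protocol and SAP*

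**What the plan says.** Section D and F1 set out a within-patient design: "an internal randomization will be performed based on breast side (left or right"). One breast receives the CDO dressing and the other the standard dressing.

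F2 and G2 make wound complications one of two primary outcomes, with tissue oxygen saturation. Hypothesis H1 in Section D is directional: "CDO adjunct therapy will reduce the likelihood of surgical wound complication including dehiscence and its volume, infection or surgical revision". Section C states a hypothesis that CDO lowers the likelihood of dehiscence and severe scarring, and adds: "We will examine the validity of this hypothesis using a pilot randomized controlled trial".

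For complications, G2 names a chi-square asking whether there are fewer incidents in the intervention group than in the control group. It names no paired method for this outcome. Its examples of the outcome include scar size beside dehiscence, infection and surgical revision.

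G1 says that n=30 "is selected based on resource/budget availability and feasibility to be completed within one year". It continues: "This sample size is estimated to be sufficient to determine feasibility and proof of concept efficacy", and describes that efficacy as improving "tissue oxygen supply and reduce likelihood of adverse events". No alpha, power, effect size, event rate or dropout is given. G1 then allows the sample to be increased later, by addendum, to validate the initial observation.

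The only event rate in the documents is in Section C: 10% to 15% for poor healing and adverse events at the T-inframammary fold.

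**The concern.** There are two separate problems.

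First, a chi-square between groups treats the 60 breasts as 60 independent units. They are 30 matched pairs. If a patient who heals poorly on one side tends to do so on the other, the test uses too large a variance for the difference. It then rejects too rarely and loses the precision that the within-patient design was meant to give.

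Second, the sufficiency statement covers a primary outcome for which very few events can be expected. A reader of G1 could take a null result as evidence of no effect, or a chance split of a handful of events as proof of concept. G1 makes a later sample increase depend partly on initial results, so such a misreading could have consequences.

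**Working it through.** **Nothing to reproduce.** G1 gives no statistical inputs for n=30, so the check asks what 30 pairs can show at the documents' own rate.

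**Inputs from the documents.** 30 patients (G1); one CDO and one control breast each (Section D, F1); control rate pc = 10% to 15% (Section C); chi-square between groups (G2).

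**Assumptions, not in the documents.** Alpha 0.05; all 30 patients analysed; the rate read per breast; one yes/no complication per breast; effect a halving (10% to 5%, 15% to 7.5%), with abolition as the extreme case; within-patient correlation rho of 0, 0.3 or 0.5.

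**Expected events.** Control: 30 × 0.10 = 3.0 and 30 × 0.15 = 4.5. CDO under a halving: 1.5 and 2.25.

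**Method.** With pt the CDO rate, the probability that both breasts have a complication is p11 = pc·pt + rho·√[pc(1−pc)·pt(1−pt)]. Control-only is pc − p11 and CDO-only is pt − p11. All possible tables for 30 pairs were enumerated exactly.

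- Chi-square, no continuity correction: z = (x − y)/30 ÷ √[p̄(1−p̄)·2/30], where x and y are the control and CDO event counts and p̄ = (x + y)/60.
- Uncorrected McNemar: z = (b − c)/√(b + c), where b and c are the control-only and CDO-only pairs.
- Reject at |z| ≥ 1.960 two-sided, or z ≥ 1.645 one-sided.

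Example, pc = 0.10, pt = 0.05, rho = 0.5: p11 = 0.005 + 0.5 × 0.0654 = 0.0377. Control-only is 0.0623 and CDO-only 0.0123, so 30 × 0.0746 = 2.2 discordant pairs are expected.

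**Results, two-sided.** Each cell gives pc = 10% / pc = 15%.

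| rho | Chi-square type I error | McNemar type I error | Chi-square power, halving | McNemar power, halving | Discordant pairs, halving |
|---|---|---|---|---|---|
| 0 | 5.4% / 5.3% | 4.8% / 4.5% | 10.6% / 15.7% | 9.9% / 13.6% | 4.2 / 6.1 |
| 0.3 | 2.2% / 2.3% | 4.1% / 4.8% | 6.5% / 11.2% | 9.5% / 17.1% | 3.0 / 4.4 |
| 0.5 | 0.8% / 0.8% | 2.6% / 4.2% | 4.0% / 7.8% | 8.2% / 18.9% | 2.2 / 3.3 |

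**One-sided.** Chi-square power for a halving is 19.4% / 25.1% at rho 0 and 10.9% / 17.1% at rho 0.5. Uncorrected McNemar gives 17% to 34% over rho 0 to 0.5.

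**Abolition of all complications.** With no CDO events, 4 against 0 gives z = 2.07 and 3 against 0 gives z = 1.78. Two-sided power is therefore the chance of at least 4 control events, 35% / 68%. One-sided it is the chance of at least 3, 59% / 85%.

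**Higher rate.** At control rates of 20% and 30% with independent breasts, two-sided power is 19% and 28% for a halving, and 88% and 99% for abolition.

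**The case against.** The strongest reply is that this is a pilot. The protocol calls itself exploratory and proof of concept throughout, promises no powered test, and separates proof of concept from later validation in G1. Judging sufficiency by the power of a significance test is a standard that the protocol did not set. This stands as far as n is concerned: a budget-based n=30 is legitimate. A reader might infer that the trial is too small and should be enlarged, but the documents do not support that. The pilot label still does not supply the estimate that G1 says was made for adverse events.

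A reader might also infer that the protocol's own rate implies power as low as 4%. It does not. That figure needs a correlation of about 0.5, which the documents do not give, as well as two-sided testing. G2 asks whether complications are fewer, which may mean a one-sided test. The effect size is likewise assumed, and abolition at the 15% rate would have 68% to 85% power.

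The base rate is imperfect. Section C counts dehiscence and thick or itchy scars, while the endpoint adds infection and revision, and per breast or per patient is not stated. A higher rate helps, but a halving stays below 30% two-sided power even at 30%.

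Finally, McNemar's test is itself of chi-square type, so G2 might be read as intending it. G2's wording compares groups and does not name it. The practical loss is bounded: the unpaired test errs on the conservative side, and the power gain from pairing is at most about 11 points in the cases examined (18.9% − 7.8%).

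**Conclusion.** Both points hold, at moderate weight.

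The pairing point follows from the design alone and needs no power target; only its size depends on the assumed correlation. It would be wrong to infer that the unpaired test inflates false positives, since under positive correlation it does the reverse. It would be equally wrong to infer that a paired test makes 30 patients sufficient for a moderate reduction: with only about 2 to 6 discordant pairs expected under a halving, it does not.

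The sufficiency point is confined to adverse events. At the documents' rate, about 3 to 4.5 control events cannot support the statement for a moderate reduction under any test examined here. Feasibility is not in question. Tissue oxygenation was not assessed, because no SD or effect is given; nothing here shows n=30 to be either adequate or inadequate for it.

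**What to change.** **G2.** Define one yes/no wound complication per breast over the 4 weeks: dehiscence, infection or surgical revision. Analyse scar size separately, as a measurement. Replace the between-group chi-square with a within-patient analysis: the paired risk difference with a 95% CI and the discordant-pair counts, with a McNemar test if a test is wanted. The endpoint definition has to come first, because a paired analysis cannot be run on a count of incidents that mixes events with a measurement.

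**G1.** Keep the budget and feasibility rationale. Remove adverse events from the sufficiency statement and describe the complication comparison as estimation. Make no new claim about tissue oxygenation. Complications may remain a primary outcome.

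**Cost.** One endpoint definition, one analysis line and a less favourable sentence in G1. No more patients and no new data are needed.
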